## **8.5 Study Termination**

NCI, DCP as the study sponsor has the right to discontinue the study at any time.

## **9. CORRELATIVE/SPECIAL STUDIES**

### **9.1 Rationale for Methodology Selection**

#### Blood

##### **miRNA analysis**

miRNA extraction and purification from serum (4.5 ml of blood) will be done accordingly to standard procedure. We will analyze approximately ~850 miRNAs using the TLDA qRT-PCR microfluidic cards (Applied Biosystems) and we will determine serum miRNA relative quantities using the  $\Delta\Delta Ct$ -method. Importantly, we will check the presence of hemolysis in all serum samples collected for miRNA screening. This will be done before the miRNA extraction by visual inspection and by measuring the absorbance at 414nm^45, and after analysis of the expression ratios of couples of miRNAs found by us and by others to be sensitive enough to reveal hidden hemolysis. In addition, we will introduce spike-in synthetic miRNAs to be used as standard references in every sample screened. This will allow us to control either the efficiency of the extraction procedure and of all the qRT-PCR reactions.

Data analysis will be performed using R software (<http://www.r-project.org/>) and SAS software (<http://www.sas.com/>) for correlation analysis with all other clinical, pathological and radiological parameters.

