## 1. OBJECTIVES

**1.1 Primary Objectives** – The primary objective is the evaluation of the effect of Aspirin as a chemopreventive agent for lung cancer. Particularly, the efficacy of Aspirin in reduction of size and number of CT-detected lung subsolid nodules will be evaluated in high-risk asymptomatic subjects currently undergoing CT screening programs at the European Institute of Oncology (EIO) and at MD Anderson Cancer Center (MDACC).

In addition, we will include subjects undergoing CT outside the context of a screening program with a subsolid nodule confirmed by pulmonary CT scan (qualifying scan).

The efficacy will be evaluated in a person-specific analysis.

**1.2 Secondary Objectives** – Secondary objective of the study will be the modulation of biological markers after treatment and the correlation of these findings with modification of lung nodules diameters. In particular we will evaluate the effect of Aspirin on a signature of serum microRNA correlated to subsolid nodules. Other secondary endpoints will be the per-lesion analysis including the evaluation of lung nodule density before and after treatment, the number and size of non target lesions including solid nodules and evaluation of response according to modified RECIST criteria. Additional biomarkers will include the modulation of ultrasensitive circulating hs-CRP, the evaluation of urinary cotinine as marker of tobacco exposure and investigation of the potential effect of aspirin according to its concentration, the measurement of urinary prostaglandin metabolites (PGEM) and leukotriene (LTE4), both normalized normalized to urinary creatinine concentration. Serum concentration of thromboxane B2 (TXB2) will be determined as a measure of compliance. We will also evaluate the tolerability of Aspirin at dose of 100 mg/day.

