### 2.3 Rationale

With the evolution of helical CT technology, CT screening for early detection of lung cancers is under evaluation in high risk individuals (former and current heavy smokers) with encouraging results. At the EIO, a single center screening trial recruited 5,202 high-risk volunteers (both current or former smokers) to undergo an annual multidetector low dose CT (ld-CT) for 5 or more years, beginning in 2004. The screening ld-CT, a non invasive test with low radiation exposure and no contrast medium, affords the opportunity to serially examine the peripheral lung for the first time, albeit with the limitation that small lesions cannot be biopsied and thus their identity remains unknown.

In September 2012, a new multicenter screening program has been launched at the EIO (Cosmos 2) with the aim of enrolling 10,000 high-risk individuals in 6 centers in Italy in a one-year period, with the goal of recruiting 5000 at the EIO. The Cosmos protocol requires once yearly low-dose CT for 5 years. One of the main objective of the study is the validation of a serum signature of 34 circulating microRNA able to predict with high sensitivity the presence of an asymptomatic lung cancer and to validate the Cosmos risk model on an independent cohort of high risk individuals to better select the target population for screening and the optimal screening interval. The population enrolled in the Cosmos 2 will represent the major source of potentially eligible subjects for the chemoprevention study.

In the meantime, two other screening programs are still ongoing at the EIO with annual ld-CT scans (Cosmos 1 and a pilot study) and they represent an additional source of potential participants.

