### Rationale for Biomarkers selection

**microRNA:** Modulation of biological markers after treatment and the correlation of these findings with modification of lung nodules diameters will be investigated as secondary endpoints. In particular, we have recently identified serum circulating microRNA (miRNA) able to accurately predict the presence of lung cancer during early stages disease. The test was accurate enough to capture the onset of the disease in patients of whom serum samples were available before and after diagnosis of lung cancer by ld-CT. The same signature was also able to identify the premalignant GGO lesions among Cosmos 1 participants (unpublished data). In brief, we screened a group of 27 individuals with GGO lung nodules and applied the miRNA test. Twenty-four out of 27 were positives to the test (~89%). Furthermore, the average miRNA-test risk score of the GGO group was 12.5 while the average score of two other groups of individuals with solid nodules (N=25), or without nodules (N=25), were -2.2 and -4.4 respectively (p <0.0001; Student's t-test). This confirmed the validity of the miRNA-test to predict the presence of GGO lesions as well as early stages lung cancer, and suggest that active or passive release in the blood of specific miRNA species is already present in lung premalignant lesions.

The advantages of such a test compared to ld-CT are the potential for an easy applicability on a population-wide scale, the high potential for implementation of screening on a nation-wide scale, the absence of risks related to ionizing radiations, and the reduced costs

As regards the technical aspects we have developed a fully automatized procedure based on low-density qRT-PCR array that allows the screening of expression of ~800 different miRNA species and using less than 300µl of serum. This will give us the opportunity to test every known miRNA present in the serum and to perform an accurate analysis of their quantities.

We intend to apply the very same technology to identify serum miRNAs predictive of the effect of aspirin treatment in patients with GGO lung nodules.

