## 13.5 Secondary Objectives, Endpoints, Analysis Plans

Generalized linear mixed models for longitudinal data will be used to compare the study groups using the standard general model  $y = X\beta + Zu + \epsilon$ , with  $y$  the response variable (e.g. secondary endpoint variable),  $X$  and  $\beta$  the design matrix and unknown parameters for the fixed effects and  $Z$  the design matrix for the random effects and  $u$  the random effects. Treatment arm (aspirin or placebo) and time visit (baseline, 6 and 12 months) will be considered fixed effects, smoking history and age at study entry random effects. Secondary endpoints include a per-lesion analysis by nodule type. Identity and logit link functions will be used for normal and binary data respectively. All tests will be two-sided and considered significant at the 5% level.

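### The search across about 800 to 850 serum miRNAs for predictors of aspirin effect has only an unadjusted 5% per-test rule, so up to about 40 chance findings are expected if every species is tested once

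*Combined protocol and SAP*

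**What the plan says.** The miRNA work has two strands.

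- **Modulation.** Section 1.2, repeated in Section 3, makes this a secondary objective: "In particular we will evaluate the effect of Aspirin on a signature of serum microRNA correlated to subsolid nodules". Section 2.3 describes a signature of 34 miRNAs, whose validation is an objective of the Cosmos 2 screening study ("validation of a serum signature of 34 circulating microRNA"). It also reports that the group's miRNA test yields a risk score, averaging 12.5 in people with ground glass opacities, -2.2 in those with solid nodules and -4.4 in those without nodules.
- **Search for predictors.** Section 2.3 (Rationale for Biomarkers selection) says the platform "allows the screening of expression of ~800 different miRNA species" and adds: "This will give us the opportunity to test every known miRNA present in the serum". It then gives the purpose: "We intend to apply the very same technology to identify serum miRNAs predictive of the effect of aspirin treatment in patients with GGO lung nodules". Section 9.1 gives the number to be assayed: "We will analyze approximately ~850 miRNAs using the TLDA qRT-PCR microfluidic cards".

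Section 8.2 lists miRNA among the secondary endpoints and sends the reader to Section 13.5 for the analysis. There the rule is: "All tests will be two-sided and considered significant at the 5% level". Sections 8.2, 9.1 and 13 contain no family-wise or false-discovery control, no locked miRNA list or score for this trial, and no statement that the screen is exploratory.

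**The concern.** A threshold of 5% per test suits one comparison. Applied to a search over hundreds of candidates, it makes chance findings certain in practice. Section 8.2 sets the ultimate goal as a non-invasive serum test that identifies subsolid nodules and predicts response to low-dose aspirin. A list of predictive miRNAs picked at 5% each would be weak ground for such a test, because the plan gives no means of judging how many entries on the list are noise.

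The signature strand carries a smaller version of the same problem. A single score would need only one test and no adjustment, but the plan never says that the score is what will be compared between the arms.

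**Working it through.** **Inputs**

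| Quantity | Value | Source |
|---|---|---|
| miRNAs assayed | about 850 | 9.1 |
| Alternative count | about 800 | 2.3, Rationale for Biomarkers selection |
| Level per test | 0.05, two-sided, unadjusted | 13.5 |
| Signature size | 34 | 2.3 (Cosmos 2) |
| Subjects per arm | 64 | 13.3 |
| Primary difference and SD | 0.8 mm and 1.6 mm | 13.3 |

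**1. The plan's own figure.** The plan gives no error rate or power for the miRNA screen. Its one calculation is for the primary endpoint: d = 0.8 / 1.6 = 0.5, which needs 63.8 per arm by the exact two-sample t-test, rounded to 64. Power at 64 per arm is 80.1%. The stated 128 reproduces, and 64 per arm is used in step 5.

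**2. Expected false positives if no miRNA is related to aspirin.** Expected count = m x 0.05.

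- m = 850: 850 x 0.05 = 42.5 (95% range 30 to 55 if the tests are independent).
- m = 800: 800 x 0.05 = 40 (28 to 52 if independent).

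The mean does not require independence. Correlation between miRNAs widens the spread around it. Nor does the mean depend on which test is used, provided each test has a true 5% level and is run once per species.

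**3. Sensitivity to detectability.** The documents give no detection rate in serum, so these are assumptions.

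- 400 detectable: 400 x 0.05 = 20.
- 200 detectable: 200 x 0.05 = 10.

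**4. The signature.**

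- One test of a pre-specified score: 1 x 0.05 = 0.05 expected false positives.
- 34 members tested one by one, for comparison only, since the plan does not propose it: 34 x 0.05 = 1.7 expected. The chance of at least one is 1 - 0.95^34 = 0.825 if independent.

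**5. Which correction.** Bonferroni over 850 gives a threshold of 0.05 / 850 = 0.000059 and cuts the expected count to 0.05. For a between-arm difference of d = 0.5 in one miRNA with 64 per arm, power falls from about 80% to about 10%. That is too strict for a discovery screen, which is why false-discovery control fits better.

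**The case against.** The strongest reply is that the plan never prescribes 850 significance tests.

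- Section 9.1 describes a laboratory platform, and its analysis text names only software and correlation analysis.
- Section 8.2 frames the miRNA endpoint as sensitivity, specificity and accuracy.
- The model in 13.5 uses three visits, whereas the schedule of events has miRNA measured at baseline and month 12 only, so 13.5 was not written around miRNA.
- The modulation objective names a signature, for which a score exists.

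On this view the analysis is under-specified rather than wrong.

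Much of this stands. No section writes out a per-miRNA comparison, so the count is conditional on that reading. Three stronger conclusions that a reader might draw are not supported:

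- **That dozens of miRNAs will be reported as modulated by aspirin.** The per-miRNA wording in 2.3 concerns prediction of the aspirin effect. The modulation objective is worded for a signature.
- **That a real signature effect would be lost among the chance findings.** The signature and its score predate this trial, so they can be examined separately from the other species.
- **That 42.5 is the number to expect, or that it should be doubled.** It requires every species to be detectable and tested once. A second family of per-miRNA tests is not written out anywhere.

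What the reply does not remove is the link within the plan. Section 2.3 states a search for individual predictive miRNAs, 8.2 routes miRNA to 13.5, and 13.5 sets an explicit unadjusted threshold for all tests. That rule, applied to that search, is unsuitable.

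**Conclusion.** The point holds in conditional form. The plan announces a discovery search over about 800 to 850 miRNAs, and its only error rule for secondary endpoints is 5% per test. If each species is tested once and none is related to aspirin, up to about 40 false positives are expected, and fewer in proportion if many species are undetectable. The modulation strand would be protected if its score were the single test, but no section says that it is.

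The conclusion rests on reading 2.3 as a miRNA-by-miRNA search and on 13.5 governing it. The consequence is confined to a secondary biomarker endpoint. The primary analysis and the sample size of 128 are unaffected. The plan should be changed, but the matter does not threaten the trial's main result.

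**What to change.** Amend Sections 8.2 and 13.5 to say:

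1. Aspirin modulation of miRNA is tested by one comparison between arms of the pre-existing signature risk score at month 12, adjusted for the baseline score, at the two-sided 5% level. The version of the score is named and locked beforehand.
2. The miRNA-by-miRNA screen is exempt from the 5% per-test rule. It is reported with Benjamini-Hochberg control at a stated false discovery rate, for example 5%, and labelled exploratory.

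The cost is wording only. miRNA is already collected at baseline and month 12, and the assays do not change. The price is that fewer individual miRNAs will be declared significant. The change does not settle how the accuracy endpoint in 8.2 is to be analysed, nor which test defines prediction of aspirin response; the sponsor would still need to write those out.

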##### **hs-CRP**

Serum concentrations of C-reactive protein as marker of inflammation will be measured by means of commercially available assays. Serum samples from the same patient obtained at different time-points will be run in batches in order to reduce analytical variability. Standards for good laboratory practice are applied. Monitoring of precision and reproducibility will be performed by processing commercially available control samples and internal in-house prepared pool of samples in each run.

#### Urine

Urine concentrations of cotinine, prostaglandin E metabolite and leukotriene E4 will be measured by

means of commercially available assays. Urine samples from the same patient obtained at different time-points will be run in batches in order to reduce analytical variability. Standards for good laboratory practice are applied. Monitoring of precision and reproducibility will be performed by processing commercially available control samples and internal in-house prepared pool of samples in each run.

### **Cotinine**

We will use NicAlert® test (Nymox Pharmaceutical Corporation, Quebec, Canada) to measure tobacco product exposure. The test is able to detect exposed to tobacco products such as cigarettes, pipes, or chewing tobacco within the past 48 hours. Second hand smoke exposure may cause a positive result in a non-user of tobacco products.

NicAlert® is a semi-quantitative immunochromatographic assay for urinary cotinine measurements, that uses monoclonal antibody-coated gold particles and a series of avidity traps that allow quantification. The sample collection end of the strip contains gold particles coated with monoclonal antibodies to cotinine, a relatively long-lived metabolite of nicotine. The distance the gold migrates on the strip is shown by a clear color change and provides an accurate measure of the amount of cotinine in the sample. The cutoff concentration for the NicAlert® test is 100 ng/mL. The NicAlert™ Negative Controls consist of cotinine-free (NicAlert® Level "0") human preserved pathogen-free urine. The NicAlert® Positive Controls consists of cotinine-free urine spiked with cotinine to concentrations of 400 ng/mL cotinine (Low Positive Control, NicAlert® level "4") and 2000 ng/mL cotinine (High Positive Control, NicAlert® level "6").

### **PGEM**

Because of the rapid metabolism of prostaglandin E2 (PGE2), the determination of the *in vivo* biosynthesis is often best accomplished by the measurement of the concentration of PGE2 metabolites. We will measure urinary concentrations of prostaglandin E metabolites (PGEM) by a competitive enzyme immunoassay (EIA) kit purchased from Cayman (Cayman Chemical Co., Ann Arbor, Michigan, United States) that converts all major metabolites into a single stable derivative which is easily measurable by EIA. The assay is based on the competition between PGE2 and PGE2-acetylcholinesterase (AChE) conjugate (PGE2 tracer) for a limited amount of PGE2 monoclonal antibody. Because the concentration of the PGE2 tracer is held constant while the concentration of PGE2 varies, the amount of PGE2 tracer that is able to bind the PGE2 monoclonal antibody is inversely proportional to the concentration of PGE2 in the well. This antibody complex PGE2 binds to goat polyclonal anti-mouse IgG that has been previously attached to the well. The plate is washed to remove any unbound reagents and then Ellmans reagent (which contains the substrate to AChE) added to the well. The product of this enzymatic reaction has a distinct yellow color that absorbs strongly at 412 nm. The intensity of this color, determined spectrophotometrically, is proportional to the amount of PGE2 tracer bound to the well, which is inversely proportional to the amount of free PGE2.

We will check for interference by contaminants present in urine by 1:10 and 1:30 dilution of crude samples with phosphate-buffered saline. If the two different dilutions of the samples show good correlation (differ by 20% or less) in the final calculated PGE2 concentration, purification is not required. If we do not see good correlation of serial dilutions, purification according to the purification protocol provided with the assay method will be applied.

### **LTE4**

Urinary leukotriene E4 (uLTE4) will be determined by a competitive enzyme immunoassay kit (Cayman Chemical Co., Ann Arbor, Michigan, United States). The assay is based on the competition between uLTE4 and uLTE4-acetylcholinesterase (AChE) conjugate (uLTE4 tracer) for a limited amount of uLTE4 Antiserum. Because the concentration of the uLTE4 tracer is held constant while the concentration of uLTE4 varies, the amount of uLTE4 tracer that is able to bind the uLTE4 antiserum will be inversely proportional to the concentration of uLTE4 in the well. This antibody uLTE4 complex binds to a mouse monoclonal anti-rabbit IgG that has been previously attached to the well. The plate is washed to remove any unbound reagents and then Ellman's reagent (which contains the substrate to AChE) added to the

well. The product of this enzymatic reaction has a distinct yellow color that absorbs strongly at 412 nm. The intensity of this color, determined spectrophotometrically, is proportional to the amount of uLTE4 tracer bound to the well, which is inversely proportional to the amount of free uLTE4.

We will check for interference by contaminants present in urine by 1:10 and 1:30 dilution of crude samples with phosphate-buffered saline. If the two different dilutions of the samples show good correlation (differ by 20% or less) in the final calculated uLTE4 concentration, purification is not required. If we do not see good correlation of serial dilutions, purification according to the purification protocol provided with the assay method will be applied.

## **TXB2**

Serum concentration of thromboxane B2 (TXB2) will be determined by a competitive enzyme linked immunosorbent assay (Neogen TM, Lexington, KY, USA). The assay is based on the competition between the enzyme conjugate and the TXB2 in the sample for a limited amount of binding sites on the antibody coated plate. The detection limit for the TXB2 assay is 4 pg/ml.

## **BIOREPOSITORY**

DNA and RNA will be prepared and stored for future unspecified analyses for specific markers for whole genome DNA and RNA profiling. Samples will be stored at IEO Biobank and Biomolecular Resource Infrastructure (IBBRI). A specific institutional informed consent will be used.

## **9.2 Comparable Methods**

We will use established and validated assays for determination of changes in biomarkers' expression in this study. We plan to evaluate biomarkers in both serum, and urine specimens for secondary endpoints evaluation. Specifically, for miRNA signature, we will use protocols developed and validated by our group within the Cosmos 1 screening program.

For serum hs-CRP and urine biomarkers (PGEM, leukotriene and cotinine) we will utilize standard protocols of commercially available kits already described in peer-reviewed publications. As to hs-CRP, our group has already published several papers involving this biomarker. Two different methods have been applied. The former was a chemiluminescent enzyme immunometric assay (Diagnostic Products Corp, Los Angeles CA) designed for the immulite automated analyzer. more recently a high sensitivity turbidimetric method for cobas integra 800 was adopted (Roche Diagnostics, Mannheim, Germany). The two methods showed an excellent correlation ( $r^2=0.99$ ).

## **10. SPECIMEN MANAGEMENT**

### **10.1 Laboratories**

The analysis of serum microRNA will be performed at the EIO laboratories of the Molecular Medicine Division (Chief [name]) under the supervision of [name].

The analysis of serum ultrasensitive hs-CRP, and urinary levels of cotinine, PGEM and LTE4 will be performed in the dedicated EIO lab of the Division of Lab Medicine under the supervision of [name], PhD.

## 10.2 Collection and Handling Procedures

All blood and urine samples will be withdrawn under fasting condition (at least 6 hours) preferably between 8 a.m. and 10 a.m. at each time point. Instructions about specimen handling and storage will be provided in a dedicated Manual of Procedures.

A total of **8 ml** of blood will be withdrawn for safety labs (at baseline, 6 and 12 months)

A total of **4.5 ml** of blood will be collected for **miRNA** (at baseline and 12 months) with the following recommendation for each blood withdrawal:

- 1) Patients should be fasting at least 6 hours before blood collection
- 2) Information about oral therapy with anti-inflammatory, anticoagulants, steroids or other drugs will be collected the same day.
- 3) Patients must have been free of any infection (including flu) and inflammatory diseases for a week prior to the collection of blood samples.
- 4) Before any instrumental or physical examination has been performed

Fasting (at least 6 hours) blood samples will be collected in all participants free of any infection (including flu) and inflammatory diseases for a week prior to the collection of blood samples at baseline and after 12 months of treatment. In order to avoid skin contamination, the first 3 mL of blood should not be used for serum preparation. Blood samples (4.5 ml) will be collected in tubes without anti-coagulant (white cap), left at room temperature for 30-60 minutes to clot, then spun at 3000 rpm (1000 g, Megafuge 2.0 – Heraeus) for 10 minutes at room temperature. The serum will be immediately removed slowly by using a plastic transfer pipette, leaving 0.5 cm remaining to avoid disturbing the serum-clot interface, dispensed in 0.6 ml aliquots (for a total of 4 aliquots) into 1.5 ml cryotubes (Thermo Fisher Scientific), specifically labeled with a barcode, and snap frozen in dry ice. Aliquots will then be transferred in a dedicated -80°C freezer.

A total of **7.5 ml** of blood will be collected into tubes containing clot activator for **hs-CRP** (at baseline, 6 and 12 months):

Morning fasting blood samples are centrifuged at 1850xg and one ml serum aliquots will be stored into 1.5 ml cryotubes (Thermo Fisher Scientific), specifically labeled with a barcode and transferred in a dedicated -80°C freezer.

A total of **7.5 ml** of blood will be collected into tubes containing clot activator for **TXB2** (at baseline, 6 and 12 months):

Morning fasting blood samples will be collected and the time of blood draw will be reported. Samples will be incubated at 25°-37°C (77-98.6°F) for 1 hour and then centrifuged at 1000xg for 7 minutes. One ml serum aliquots will be stored into 1.5 ml cryotubes (Thermo Fisher Scientific), specifically labeled with a barcode and transferred in a dedicated -80°C freezer.

First morning **urine** samples (**15 ml**) should be collected under fasting conditions following the standard procedure for appropriate urine collection (may be provided) and samples should be kept refrigerated until arrival to hospital. Alternatively, samples should be collected under fasting conditions (15 ml) at the hospital in concomitance with blood draw. Urinary creatine will be determined on fresh specimen to normalize subsequent urinary biomarker results. The remaining sample will be aliquoted into 2.0 ml cryotubes, specifically labeled with a barcode and transferred in a dedicated -80°C freezer.

A total **2.5 ml** whole blood will be collected at baseline and 12 months of treatment in tubes containing

anti-coagulant CBC - Na-EDTA (red cap) and stored at -80°C in order to collect DNA and RNA for future unspecified analysis.

DNA will be purified using the QIAamp DNA Blood Mini Kit (QIAGEN) that is designed for processing up to 200 µl fresh or frozen human whole blood with an expected yield of 4-12ug of DNA, which is sufficient for all downstream sequencing and PCR analyses. RNA will be purified using the QIAamp RNA Blood Mini Kit (QIAGEN) specifically designed for extracting high-quality RNA (1-5ug yeald) for all low- and high-throughput screening technologies (qRT-PCR, microarray, RNA-seq).

All DNA/RNA samples will be stored at -80°C in the IEO biobank (IBBRI).

